Table 2: Schedule of study procedures for participants enrolled in the asymptomatic TB transmission in Indonesia and South Africa study.....	24
Table 3: Assumptions used to determine overall scale of screening and power for the asymptomatic TB transmission in Indonesia and South Africa study	36
Table 4: Minimum risk difference that can be detected in each site with 80% power, comparing aTB and control households	37
Table 5: Relative reduction that can be excluded with 80% power, comparing aTB and sTB households ¹	38
Table 6: TB notifications and estimated TB Burden in Indonesia and South Africa in 2023 ¹	53
Table 7: Schedule of Study Procedures.....	54

LIST OF ACRONYMS AND DEFINITION OF TERMS

ACRONYMS

AHRI	Africa Health Research Institute
ART	Anti-retroviral therapy
aTB	Asymptomatic TB
aTB-C	Asymptomatic TB - Confirmed
aTB -U	Asymptomatic TB - Unconfirmed
dCXR/CAD	Digital Chest X-Ray with Computer-Aided Detection
DNA	Deoxyribonucleic Acid
EBC	Exhaled Breath Condensate
HH	Household
IGRA	Interferon-Gamma Release Assays
KZN	KwaZulu-Natal
LAM	Lipoarabinomannan
MGIT	Mycobacteria Growth Indicator Tube
mRNA	Messenger Ribonucleic Acid
Mtb	Mycobacterium tuberculosis
NHLS	National Health Laboratory Service
NHREC	National Department of Health Ethics in Health Research
NAAT	Nucleic Acid Amplification Test
PCR	Polymerase Chain Reaction
RC3ID	Research Center for Care and Control of Infectious Disease
sTB	Symptomatic TB
sTB-C	Symptomatic TB - Confirmed
sTB-U	Symptomatic TB - Unconfirmed
QGIT	QuantiFERON Gold In-Tube
TB	Tuberculosis
TPT	TB Preventative Therapy
TST	Tuberculin Skin Tests
W4SS	WHO 4 Symptom Screen
WHO	World Health Organisation
Xpert	Xpert MTB/RIF Ultra

DEFINITIONS

Term	Definition
W4SS (WHO-recommended Four Symptom Screen)	A symptom-based screening tool recommended by the World Health Organization for tuberculosis (TB) screening. It involves asking about (i) cough of any duration, (ii) fever, (iii) night sweats, or (iv) unexplained weight loss. In children the W4SS is adapted to include (i) cough of any duration (ii) fever (iii) poor weight gain or weight loss (iv) close contact with a person with TB disease.
W4SS Screen-positive	An individual who reports one or more symptoms on the W4SS
W4SS Screen-negative	An individual who reports all four W4SS symptoms are absent (regardless of whether they have other TB symptoms)

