Based on data from a health and demographic surveillance system in northern KZN, children aged 2-14 years old are 32.0% of the resident population, and 39.8% of households have at least one resident child in this age group. In the households with children in this age group, the median number of children per household is 2 (IQR 1-3) and mean is 2.58 (SD=1.63). A study done across two provinces (Limpopo and Free State) showed tuberculin skin test positivity of 17%.³⁰ The recently completed (not published) household (HH) contact tracing conducted in the Hlabisa sub-district in northern KZN found 18.4% (95% CI:15.-21.5%) IGRA positivity in child contacts of symptomatic clinic diagnosed people with TB. The IGRA positivity was 16.4% (95% CI: 7.8%-28.8%) amongst child contacts of people with aTB diagnosed at the clinic and 7% (95% CI: 3.5% to 10.5%) in community controls with no person with TB in the household.

In Bandung city, 59.0% of households have at least one child aged 2-14 years, with a mean of 1.5 (SD=0.7). In a study comparing IGRA and TST in Bandung City in 196 households with a person with TB, 299 household-exposed children aged 6 months to 9 years old and 72 age and sex matched neighbourhood-exposed children were recruited and tested. Of the household contacts, 156 (52%) tested positive using IGRA and 144 (48%) using TST³¹. Of the neighbours 15 of 72 tested (21%) were IGRA positive and 7 (21%) were TST positive. Of 38 children with a follow-up IGRA test at 3 months, 8 of 23 (35%) initially IGRA negative individuals had IGRA conversion and 3 of 15 (20%) initially IGRA positive individuals had IGRA reversion. Another study recruited 1,347 TB household contacts of 462 known TB

cases³². Of the contacts, 170 were children aged 5 to 9 years; 96 of 168 (57%) tested were IGRA positive among the children, and a further 15 amongst 67 (22%) tested after 14 weeks became IGRA positive amongst the 72 who were initially IGRA negative.

INTERFERON-GAMMA RELEASE ASSAY

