3.4 STUDY SCHEDULE

A summary of study visits is provided in **Table 2**, and the flowchart of Schedule of Procedures is presented in **Appendix C**.

Table 2: Schedule of study procedures for participants enrolled in the asymptomatic TB transmission in Indonesia and South Africa study

Cross-sectional study of Household Mtb	
Visit 0: Household identification and consent
 
 • Identify geospatial areas for enumeration • Informed consent by household head • Minimal Household enumeration to determine eligibility • Dwelling/House description data
--	--

infection (core study)	
Visit 1: Screening and enrolment
 
 • Consent and enrolment of all adolescents and adults HH members • Demographics • Basic Health Questionnaire • Symptom screening (including W4SS) • Minimal physical examination (weight, height) • Sputum collection for Xpert and MGIT culture • Tongue swab NAAT collection for participants unable or refuse to produce sputum[#] • Digital chest x-ray with computer aided detection (dCXR/CAD) 
Visit 2.1 and 2.2: Community or clinic IGRA measurements (weeks 0-2 and or 8-10)
 
 • Individual assent and parent/ guardian consent for child household contacts • Structured questionnaire on contact patterns with index person and detailed dwelling/House description data • Symptom screening (W4SS modified for children) • If TB symptoms, sputum collection • Weight, height, mid upper arm circumference (MUAC) • Venous blood for IGRA testing (all children at visit 2.1; at week 8-10 (visit 2.2), only repeat IGRA if visit 2.1 IGRA was negative) • Venous blood samples -for HIV^{\$}, cell-free Mtb DNA, Mtb-specific T cells and biobanking • If any symptoms or signs suggestive of TB are identified, refer to the appropriate health facility and provide support for TB investigation and treatment in accordance with national guidelines • Referral for TB preventative therapy (TPT) for all HH contacts of people with TB (visit 2.2) 
Visit 2.3: Community, clinic or telephonic review and referral (weeks 2-14), Provide IGRA status
 
 • Issue any outstanding results for adults • Follow-up on TB treatment or TPT initiation • End of study visit for cross-sectional study

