Most participants will be categorized according to their screening results which include Xpert or tongue swab NAAT and dCXR/CAD. These results are expected to be available within approximately two weeks of sample collection. The **MGIT culture results** may require up to 6 weeks to become available.-Those participants that are newly diagnosed with TB (as aTB-C, sTB-C) based on the MGIT culture results will be considered for the sub-study 1 and 2; while their child household contacts will be invited to undergo IGRA assessments. If the adolescent or adult MGIT result is positive within 2 weeks of collection, the child HHC will be invited to participate in visits 2.1 and 2.2. If the MGIT result becomes positive later than 2 weeks, only visit 2.2 will be conducted, due to study visit scheduling constraints.

All adolescent/adult participants with positive screening results (Xpert; tongue swab, MGIT) will be referred to Visit 1.1 within 2 weeks of their positive result and will receive appropriate referrals at the end of the study visit. Participants who are not eligible for any additional study visits will have their screening results returned, appropriate referrals will be made as needed, and participants will be thanked for their participation. When all results are normal and no referrals are required, participants may be informed of their results by telephone or SMS.

Households of **aTB-C participants (aTB-C household)** and **sTB-C participants (sTB-C household)**, as well as selected **noTB participants (Control Household)** serving as controls, will undergo a follow-up visit (Visit 2.1).

At the **community or clinic visit (visit 2.1; Figure 3)**, if the child or children meet the eligibility criteria, initially parental/individual assent and/or guardian consent will be obtained for each child during this visit.

Figure 3. Core study participant flow, including IGRA testing among child contacts.

★ If the adolescent/adult MGIT is positive within 2 weeks, the child household contact will be eligible for both visit 2.1 and 2.2

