3.8 STUDY OUTCOMES/ ANALYSES

The study is designed to assess both the transmission of Mtb within households and the diagnostic performance of current and novel tools for detecting asymptomatic TB. The outcomes are grouped into primary and additional outcomes categories as outlined below.

CORE STUDY

Primary endpoint: Cumulative prevalence of child household contact IGRA positivity or confirmed TB (TB-C) at 10 weeks after diagnosis of the index case.

Additional outcomes/ analyses:

- (1) Proportion of children that convert from negative IGRA status at baseline to a positive IGRA status at 10-week visit.
- (2) Proportion of children with a positive plasma cell free Mtb DNA assay and positive Mtb-specific T cell activation assay, stratified by household group.
- (3) Whole genome sequencing of Mtb isolates from people with TB-C and household contacts.

CASE-CONTROL PHENOTYPING STUDY (SUB-STUDY 1)

- (4) Sensitivity, specificity, positive predictive value, negative predictive value, yield, feasibility, acceptability of digital chest x-ray with computer aided diagnosis (dCXR/CAD), sputum Nucleic Acid Amplification Test (NAAT), Mycobacteria Growth Indicator Tube (MGIT), tongue swab NAAT, and bioaerosol collection facemask mask NAAT to detect aTB-C.
- (5) Symptoms, health outcomes quality of life, comorbidities, nutritional status, and TB history, relative to group and W4SS status at screening.

(6) Proportion and characteristics of participants with detectable exhaled breath condensate lipoarabinomannan (LAM), positive plasma cell free Mtb DNA assay, positive Mtb-specific T cell activation assay and additional blood-based TB biomarkers, stratified by group.

TB UNCONFIRMED (TB-U) COHORT (SUB-STUDY 2)

(7) Time to event and factors associated with microbiological or clinical progression in participants with initially untreated aTB-U.

(8) Plasma biomarkers (including cell free Mtb DNA, Mtb-specific T cells, transcriptional signatures) that correlate with progression from aTB-U in the 12 months after TB screening

(9) Proportion and characteristics of participants with TB screening results suggestive of (TB-U) who have a subsequent positive sputum GeneXpert Ultra, sputum MGIT, tongue swab NAAT or Bioaerosol collection facemask mask NAAT.

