APPENDIX C : SCHEDULE OF STUDY PROCEDURES

Table 7: Schedule of Study Procedures

Study	Cross- Sectional study (core study)					Phenotypic (Sub-study 1)	Cohort (Sub-study 2)			
	Adolescents & Adults (> 15 yrs.)		Children (2-14 years)				Adolescents & Adults			
Visit	Visit 0	Visit 1	Visit 2.1	Visit 2.2	Visit 2.3	Visit 1.1	Visit 1.2	Visit 1.3	Visit 1.4	Visit 1.5
Time point		screening	Week 0-2*	Week 8-10	Week 2-14	Week 1-8	Month 3	Month 6	Month 9	Month 12
Household census and consent	x									
Informed consent / assent		x	x	x ^b		x				
Demographics		x								
Medical History		x				x				
Structured questionnaire			x	x ^b		x				
TB Symptom Screening (W4SS)		x	x	x						
TB Symptom Assessment (full)						x	x	x	x	x
Clinical Assessment incl. quality of life, functional status							x	x	x	x
Physical Examination -limited		x	x	x ^b						
Physical Examination - full						x	x	x	x	x
Sputum sampling – NAAT & MGIT		x	x ^a	x ^a		x	x	x	x	x
Blood sample- HIV Counselling and testing\$			x	x ^b		x				
Blood sample- IGRA			x	x ^c						
Blood sample – HbA1c, full blood count						x				
Blood sample – Mtb-specific T cell activation; Mtb cell free DNA; biobanking			x	x		x	x	x	x	x
Digital X-Ray with CAD		x					x	x	x	x
Novel tests – tongue swab NAAT; facemask; exhaled breath condensate						x	x ^d	x ^d	x ^d	x ^d
Physician review						x	x	x	x	x
Referral to DOH – TB assessment, as required			x	x	x	x	x	x	x	x
Referral to DOH – TPT, as required			x	x	x					

x^a: if child is symptomatic; **x^b:** if adult diagnosed on MGIT> 2 weeks after collection, child consent/assent, structured questionnaire and HIV will be taken at visit 2.2; **x^c=** : IGRA repeated at visit 2.2 if negative at visit 2.1 **x^d:** facemask and exhaled breath condensate to be collected at all study visits in a subset of TB-U cohort participants (first n=100); * If adolescent/ adult MGIT positive within 2 weeks the child HHC will be eligible for visit 2.1 & 2.2; if MGIT positive> 2weeks, the child HHC will only attend visit 2.2; \$: HIV testing of children will only occur in South Africa

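### The cumulative 10-week primary endpoint rests on one IGRA in late-MGIT households and up to two elsewhere, with week 0 undefined and no schedule stated for matched controls

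*Protocol*

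**What the plan says.** Section 3.8 defines the core-study endpoint as "Cumulative prevalence of child household contact IGRA positivity or confirmed TB (TB-C) at 10 weeks after diagnosis of the index case". The protocol summary gives the same time point.

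Section 3.4 (Table 2) heads visits 2.1 and 2.2 "Community or clinic IGRA measurements (weeks 0-2 and or 8-10" and limits the second blood test: "only repeat IGRA if visit 2.1 IGRA was negative". A positive at either visit therefore counts. Section 3.5 counts visit 2.2 as 8-10 weeks after the baseline test.

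MGIT results "may require up to 6 weeks to become available" (Section 3.5). For index cases found by MGIT after the first two weeks, Section 3.5 says "If the MGIT result becomes positive later than 2 weeks, only visit 2.2 will be conducted, due to study visit scheduling constraints", and the Appendix C footnote repeats it: "if MGIT positive> 2weeks, the child HHC will only attend visit 2.2".

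The Background reports early IGRA reversion in case contacts in general. For Bandung children it says "3 of 15 (20%) initially IGRA positive individuals had IGRA reversion", with 35% conversion among those first negative.

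Section 5.2 discusses misclassification from infection outside the household and between symptom groups. It does not mention the number or timing of IGRAs.

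On the confirmed-TB component, the Definitions list "iv) close contact with a person with TB disease" as an item of the child symptom screen, and one item makes a person screen-positive. Sections 3.4 and 3.5 and Appendix C trigger child sputum on symptoms.

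**The concern.** A cumulative endpoint depends on how often and when it is looked for. A child tested twice can be counted through an early positive that later reverts or through a later conversion. A child tested once can be counted only for what is present that day. Here the number of tests depends on how and when the index adult was diagnosed, which is tied to exposure group.

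For the first co-primary contrast, the one-test path is written only for households with a culture-positive adult, and the schedule for the controls matched to them is not stated. For the second, nothing makes late culture diagnosis equally common in aTB-C and sTB-C.

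Later analysis cannot fully repair this. Baseline positives are not retested, so a common single-test endpoint at visit 2.2 cannot be built for all children. One-test children also have no baseline for the conversion outcome in Section 3.8.

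**Working it through.** **1. Does the schedule deliver the stated 10 weeks?** Inputs: visit 2.2 at weeks 8-10 (Section 3.4); MGIT positive after more than 2 and up to 6 weeks (Section 3.5).

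Weeks from diagnosis to visit 2.2 = visit week minus diagnosis week. With week 0 at screening:

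| Index diagnosis | Earliest | Latest | IGRAs |
|---|---|---|---|
| Within 2 weeks | 8 − 2 = 6 | 10 − 0 = 10 | up to 2 |
| MGIT, weeks 2 to 6 | 8 − 6 = 2 | 10 − 2 = 8 | 1 |

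The 10 weeks can be reached in the first row and never in the second.

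**2. Which clock?** No section defines week 0. The screening clock fits visit 1.1: up to 6 weeks for MGIT plus referral within 2 weeks gives week 8, the end of its weeks 1-8 window. It also explains why scheduling would rule out visit 2.1 for late results. If instead weeks ran from diagnosis, the single test would fall at 8-10 weeks as the endpoint needs, which is 2 + 8 = 10 to 6 + 10 = 16 weeks after screening. For a week-6 result that is weeks 14-16, at or past the end of the visit 2.3 window (weeks 2-14). One test versus two remains on either clock.

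**3. Illustration of size, reversion only.** Inputs from the Background (Bandung): 52% positive at baseline, 35% conversion, 20% reversion at 3 months.

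- Two tests: 0.52 + 0.48 × 0.35 = 0.688.
- One later test: 0.52 × 0.80 + 0.48 × 0.35 = 0.584.
- Relative loss: 1 − 0.584/0.688 = 0.15.

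Let f be the share of aTB-C households that are late-MGIT. The protocol gives no figure, so f = 0.1 to 0.4 is assumed. Table 4 sets Bandung at 32% versus 20%, a 12-point difference. If controls keep two tests:

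- f = 0.1: 0.32 × 0.15 × 0.1 = 0.48 points, 4% of 12.
- f = 0.4: 0.32 × 0.15 × 0.4 = 1.92 points, 16% of 12.

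**4. How firm is that?** Reversion of 3/15 has an exact 95% interval of about 4-48%. Relative loss is then 0.52 × 0.04/0.688 = 3% to 0.52 × 0.48/0.688 = 36%. Over the same f, the loss runs from 0.32 × 0.03 × 0.1 = 0.1 to 0.32 × 0.36 × 0.4 = 4.6 points.

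Holding reversion at 20% and letting the share s of eventual positives already positive at baseline run from 0.5 to 1 (assumed), loss = P × f × s × 0.20:

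- Bandung, P = 0.32: 0.3 to 2.6 points, so 12.0 is observed as 11.7 to 9.4.
- KwaZulu-Natal, P = 0.14: 0.1 to 1.1 points, so 7.0 is observed as 6.9 to 5.9.

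**5. Second contrast.** Observed ratio = true ratio × (1 − f_a × s × 0.20)/(1 − f_s × s × 0.20), where f_a and f_s are the late shares in aTB-C and sTB-C. A true ratio of 1.00 becomes:

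- f_a = 0.2, f_s = 0.1, s = 0.5: 0.98/0.99 = 0.99.
- f_a = 0.4, f_s = 0.1, s = 1: 0.92/0.98 = 0.94.

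If late diagnosis is commoner in sTB-C, the bias reverses and favours the non-inferiority conclusion.

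**The case against.** Several stronger readings are tempting, and the protocol does not support them.

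*The single test is too early.* This holds only on a screening clock, which is inferred. The endpoint counts from diagnosis and Section 3.5 counts visit 2.2 from baseline. The screening clock has its own difficulty: categorisation takes up to 2 weeks, leaving little room for visit 2.1 in weeks 0-2. What stands is that the clock is undefined and the better-supported reading conflicts with the endpoint.

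*Controls get more tests than aTB-C households.* Section 3.5 lists control households for visit 2.1, but a control drawn for an index case found in weeks 3-6 may meet the same scheduling limit. The protocol does not say, and the IGRA flow figure is not reproduced in the text available. What stands is a missing rule, not a shown imbalance.

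*The risk difference is biased downwards by a known amount.* Reversion rests on 15 children from a follow-up subset aged 6 months to 9 years, tested at 3 months. The late share is assumed, and Section 3.5 says most participants are categorised on screening results. Longer untreated exposure before a late diagnosis could raise positivity and offset the loss.

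*Every child in a TB household will have sputum taken.* The operative sections speak of symptoms, and contact is not a symptom. This is an ambiguity between the Definitions and the procedures. It would act alike in aTB-C and sTB-C households, so it bears mainly on the control contrast.

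It can also be said that sensitivity analyses belong in the SAP, which is not at hand. That is fair for the analysis, but the visit schedule is fixed in the protocol.

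**Conclusion.** The point holds as unequal ascertainment of the primary endpoint: one IGRA for children of late-MGIT index cases, up to two for others, with week 0 undefined and no schedule given for the matched controls. On the screening clock the single test falls 2-8 weeks after diagnosis, against the endpoint's 10. Both co-primary contrasts can be affected.

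The size cannot be established from the protocol. The illustration of 0.5-1.9 points out of 12 assumes 10-40% late-MGIT households, 20% reversion and two tests in controls. It leaves out any loss from testing before conversion and any gain from longer exposure. Net direction is therefore not certain, though under-ascertainment in late-MGIT households is the likelier result. The matter should be settled before child testing starts, because missing tests cannot be recovered.

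**What to change.** 1. Define week 0 as the date of the index result and, for controls, the date of their matched index case's result. Reconcile the visit 2.2 window with the 10 weeks after diagnosis in the endpoint.
2. Give controls matched to a late-MGIT index case the same IGRA schedule as that index household. This makes testing comparable within matched sets; it does not equalise aTB-C with sTB-C.
3. Pre-specify a sensitivity analysis of both co-primary contrasts that excludes one-test households and their matched controls. Read it with care: these are culture-only index cases, likely of lower bacillary burden, which Section 5.2 treats as a possible mediator. For the same reason, a visit-pattern covariate in the main model is not advised.
4. Reconcile the contact item in the child symptom-screen definition with the symptom-based sputum trigger in Sections 3.4 and 3.5 and Appendix C, so that finding confirmed TB does not depend on household group.

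Cost: a visit-window amendment, later visits for a subset that overlap the visit 2.3 window, and one added analysis. Table 2 lists the TPT referral at visit 2.2, so its timing must be reconciled with any moved window. Adding visit 2.1 for late-MGIT households would equalise the number of tests but needs further field resources.
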